8.3 Leukapheresis Visit (must occur within 3 weeks after biopsy)

Leukapheresis: Leukapheresis for AGS-003 manufacturing should be performed 3 weeks after tumor biopsy. Scheduling of leukapheresis will be determined by American Red Cross availability. Patient may need second leukapheresis based on success of first one. All efforts will be made to ensure that second leukapheresis will be within the 3 week timeframe but will not be considered a protocol deviation if it falls out of this window.

8.4 AGS-003 Treatment Phase

The manufacturing of the vaccine can take 6-12 weeks. Due to the unexpected nature of the timeline of manufacturing, once the vaccine has been successfully created and ready to be shipped to RPCI, the study coordinator will work with Argos and all site staff to ensure that scheduling for proper administration and safety testing is performed. Injections should be given 7 days apart. Shipments are sent from Argos one dose at a time. Shipment delays and other unexpected events do occur therefore a dosing window of +/- 2 days will be allowed for each dose.

8.4.1 Injection Week #1

- Vital Signs, weight
- ECOG Performance Status
- Concomitant medications
- Adverse events
- Hematology, Chemistry, Autoimmune and Immunologic assessment prior to dosing
- Administer AGS-003, 1st dose

8.4.2 Injection Week #2

- Vital Signs, weight
- ECOG Performance Status
- Concomitant medications
- Adverse events
- Administer AGS-003 2nd dose

8.4.3 Injection Week #3

- Vital Signs, weight
- ECOG Performance Status
- Concomitant medications
- Adverse events
- Hematology, Chemistry, and Autoimmune assessment prior to dosing
- Administer AGS-003 3rd dose

8.4.4 Nephrectomy Visit

Partial or radical nephrectomy will be performed at this visit.

The following assessments are also performed at this time. If there is a pre-operative visit, the assessments may be performed as part of that visit instead. Otherwise, assessments are to be performed on day of scheduled nephrectomy, prior to surgery.

- Concomitant medications
- Adverse events
- Blood draw for Immunologic assessment
- Blood draw for Hematology, Chemistry and Autoimmunity assessment
- Tissue sample from nephrectomy.

8.5 End of Study Visit/ Follow-Up

The end of study visit is conducted approximately one month following nephrectomy, or any time the subject discontinues the study. The following assessments will be performed:

- Physical examination including vital signs and weight
- Hematology: Complete Blood Count with automated differential (CBC/DIFF)
- Chemistry: Complete Metabolic Panel (P22 COMP)
- Blood draw for Immunological analysis
- Blood draw for Autoimmunity assessment
- Pregnancy test (urine) in females of childbearing potential
- ECOG Performance Status (see **Appendix A**)
- Concomitant medication
- Adverse events (surgical AEs only if clinically significant)

8.6 Schedule of Procedures and Observations

The schedule of procedures and observations for this study is summarized in **Table 1**.

Table 1. Schedule of Procedures and Observations

	Screening ¹	Leukapheresis Visit	Injection Week #1	Injection Week #2	Injection Week #3	Nephrectomy Visit	End of Study/ Follow -Up ³
Medical History	X						
Physical Examination	X						X
Vital Signs & ECOG ¹³	X		X	X	X		X
Prior/Concomitant Medications	X ⁴		X	X	X	X	X
Adverse Events			X	X	X	X	X
Chemistry ⁵	X		X		X	X	X
Hematology ⁶	X		X		X	X	X
Autoimmunity Assessment ⁷	X		X		X	X	X
Pregnancy Test (urine) ⁸	X						X
Tumor Assessment ⁹	X						
Tumor Biopsy for AGS-003	X						
Leukapheresis for AGS-003 ¹⁰		X					
AGS-003 Dose ¹¹			1 st	2 nd	3 rd		
Blood Sampling for Immunologic Assessment ¹²			X			X	X
Nephrectomy						X	
Tissue from Nephrectomy						X	

Notes for Table 1

1. Performed within 4 weeks prior to Leukapheresis Visit.
2. If there is a pre-operative visit, Nephrectomy Visit assessments may be performed as part of that visit instead. Otherwise, assessments, including immunologic, are to be performed on day of nephrectomy prior to surgery.
3. Performed at post op visit following nephrectomy, or if subject discontinues or is withdrawn from the study.
4. Medications ongoing within 1 week prior to tumor biopsy.
5. **Chemistry:** Complete Metabolic Panel (i.e., CMP: chloride, CO₂, potassium, sodium, BUN, glucose, calcium, creatinine, total protein, albumin, bilirubin total, alkaline phosphatase, AST, ALT, osmol (calc), anion gap, B/C ratio, A/G ratio) along with gamma-glutamyl transferase (GGT), lactose dehydrogenase (LDH), phosphorus, magnesium, uric acid, thyroid stimulating hormone (TSH), c-reactive protein (CRP), and corrected calcium. NOTE: On Injection Weeks #1 and #3 assessments should be taken prior to dosing. At Nephrectomy Visit the assessments can be taken either at a pre-operative visit or on the day of nephrectomy prior to surgery.
6. **Hematology:**[(i.e., complete blood count (CBC) with automated differentials): WBC, RBC, HGB, HCT, platelet, MCV, MCH, MCHC, %neutrophils, absolute neutrophils, %monocytes, absolute monocytes, % eosinophils, absolute eosinophils, %basophils, absolute basophils, %lymphocyte total, absolute lymphocyte total, platelet confirmation as clinically indicated. Grade 4 neutropenia should be monitored according to institutional guidelines. NOTE: On Injection Weeks #1 and #3 assessments should be taken prior to dosing. At Nephrectomy Visit the assessments can be taken either at a pre-operative visit or on the day of nephrectomy prior to surgery.
7. On Injection Weeks #1 and #3 assessment should be taken prior to dosing. At Nephrectomy Visit the assessment can be taken either at a pre-operative visit or on the day of nephrectomy prior to surgery: Rheumatoid Factor (RF), Anti-thyroglobulin (TG), Anti-double stranded DNA antibody (dsDNA antibody), Anti-nuclear antibody (ANA).
8. Only applicable to females of child-bearing potential.
9. To include CT scan of the chest, abdomen, and pelvis.
10. American Red Cross ([name]) in accordance with Argos requirements. Should not be performed less than 48 hours after tumor biopsy procedure.
11. Perform any required Chemistry, Hematology, Autoimmune and Immunologic assessment blood draws **before** AGS-003 dosing. Observe possible Injection Site Reactions for 1 hour post injection. Assess Vital signs (temperature, heart rate, respiration rate, BP). The target dose of AGS-003 (1.2×10^7 DCs) is delivered in three intradermal injections of 0.2 mL each (0.6 mL total volume) at Injection Weeks #1, #2, and #3 (every 7 days, \pm 2 days).
12. For *Argos Immune Monitoring*: Six, 10 mL green-top heparinized collection tubes, (tubes provided in kit). Refer to **Section 9.1.1**. For *Correlative Studies Samples*: Four, 10 mL green-top heparinized collection tubes: **Refer to 9.1.2**.

13. Screening vital signs: temperature, heart rate, respiration rate, BP, height and weight.
Dose days and End of Study: all but height.

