Objectives	Primary: To assess the immune-modulatory systemic and intratumoral effects of AGS-003as neoadjuvant treatment in patients with localized renal cell carcinoma. Secondary: To assess the feasibility that total tumor RNA processing-related activities meet specifications for AGS-003 manufacturing utilizing a core needle biopsy procedure for tumor harvesting prior to nephrectomy.
Study Design	This is a non-randomized single center pilot trial, treating patients who are eligible to undergo a partial or radical nephrectomy with the autologous AGS-003 immunotherapy in a neoadjuvant fashion prior to surgery. Peripheral (blood) and intratumoral parameters will be assessed.
Target Accrual & Study Duration	A maximum of 10 patients at RPCI will be enrolled. Study accrual is expected to take 4 years. Patients will participate in this study for approximately 6 months from the time of consent through final study visit.
Study Procedures	Disease Evaluation: Screening. Adverse Events assessments: Throughout the study. Hematology and Chemistry: Screening, Injection Week #1, Injection Week #3, Nephrectomy Visit, and End of Study. Autoimmune Assessment: Screening, Injection Week #1, Injection Week #3, Nephrectomy Visit, and End of Study. Immunologic Analysis Blood Draw: Injection Week #1, Nephrectomy Visit, and End of Study. Pregnancy Test (urine) in females of childbearing potential: Screening and End of Study. Performance Status: Screening, Injection Week #1, Injection Week #2, Injection Week #3, and End of Study. Physical Examination: Screening and End of Study. Tumor biopsy for manufacture of AGS-003: Screening. Leukapheresis for manufacture of AGS-003: Leukapheresis Visit (must be at least 48 hours between tumor biopsy and leukapheresis) AGS-003 Dosing: Once-weekly dosing beginning at Injection Week #1 for

	3 weeks.

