5.2 Exclusion Criteria

Patients will be excluded from this study for the following:

1. Patients who have had chemotherapy or radiotherapy within 4 weeks (6 weeks for nitrosoureas or mitomycin C) prior to entering the study or those who have not recovered from adverse events due to agents administered more than 4 weeks earlier.
2. Uncontrolled intercurrent illness including, but not limited to, ongoing or active infection, symptomatic congestive heart failure (e.g., shortness of breath, fatigue, orthopnea, paroxysmal nocturnal dyspnea), unstable angina pectoris, cardiac arrhythmia, or psychiatric illness/social situations that would limit compliance with study requirements.
3. Radiation to primary tumor prior to enrollment in this study.
4. Pregnant or nursing female patients.
5. Unwilling or unable to follow protocol requirements.
6. Active autoimmune disease or condition requiring chronic immunosuppressive therapy (e.g., rheumatoid arthritis, systemic lupus erythematosus, multiple sclerosis, organ transplant recipient, etc.).

- NOTE: Abnormal laboratory values for autoimmunity markers in the absence of other signs/symptoms of autoimmune disease are not exclusionary.
- 7. Known clinically significant infections, including human immunodeficiency virus (HIV) and active hepatitis B or C
- 8. Any condition which in the Investigator's opinion deems the patient an unsuitable candidate to receive treatment (i.e., any significant medical illness or abnormal laboratory finding that would, in the investigator's judgment, increase the subject's risk by participating in this study).
- 9. Chronic use of systemic corticosteroids (i.e., ≥ 10 mg/day prednisone or equivalent).
- 10. Received an investigational agent within 30 days prior to enrollment.

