6.1.2 Leukapheresis

The AGS-003 manufacturing process requires leukapheresis to collect autologous leukocytes. Study patients will be referred to the American Red Cross in Buffalo ([name]). Even though leukapheresis occurs prior to administration of investigational product, RPCI will report to the FDA severe (Grade 3, CTCAE) or life-threatening (Grade 4, CTCAE) events associated with the leukapheresis.

The leukapheresis should not be performed less than 48 hours after the tumor biopsy procedure (Section 6.1.1).

In most cases, only a single leukapheresis will be required to support product manufacture. However in some cases, cellular collection or manufacturing with the initial product is unsuccessful, and a second or third leukapheresis may be required. If additional leukapheresis (es) is required, standard treatment should still be initiated as clinically indicated.

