8.2 Screening

The following evaluations will be performed within 4 weeks prior to tumor biopsy:

- Medical history (including all prior anti-tumoral therapy related to RCC)

- Physical examination, including vital signs (i.e., temperature, heart rate, respiratory rate, blood pressure), body weight, and height
- Hematology:
 - (i.e., complete blood count (CBC) with automated differentials): WBC, RBC, HGB, HCT, platelet, MCV, MCH, MCHC, %neutrophils, absolute neutrophils, %monocytes, absolute monocytes, %eosinophils, absolute eosinophils, %basophils, absolute basophils, %lymphocyte total, absolute lymphocyte total, platelet confirmation (as clinically indicated), and differential confirmation (as clinically indicated).
- Chemistry:
 - Complete Metabolic Panel (i.e., CMP: chloride, CO₂, potassium, sodium, BUN, glucose, calcium, creatinine, total protein, albumin, bilirubin total, alkaline phosphatase, AST, ALT, osmol (calc), anion gap, B/C ratio, A/G ratio) along with gamma-glutamyl transferase (GGT), lactose dehydrogenase (LDH), phosphorus, magnesium, uric acid, thyroid stimulating hormone (TSH), c-reactive protein (CRP), and corrected calcium.
- Autoimmunity Assessment:
 - Rheumatoid factor (RF)
 - Anti-thyroglobulin antibody (TG)
 - Anti-double stranded DNA antibody (dsDNA antibody)
 - Anti-nuclear antibody (ANA)
- ECOG Performance Status (see **Appendix A**)
- Tumor assessment, including CT scan of the chest, abdomen, and pelvis
- Concomitant Medications List any ongoing medications with an onset within 1 week of tumor biopsy
- Pregnancy test (urine) in females of childbearing potential

Tumor biopsy for AGS-003 in accordance with Argos requirements will also be performed at Screening.

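### Screening is anchored to biopsy in Section 8.2 but to leukapheresis in Table 1, and no pregnancy test is scheduled between Screening and the first dose

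*Combined protocol and SAP*

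**What the plan says.** **Screening window.** Section 8.2 reads: "The following evaluations will be performed within 4 weeks prior to tumor biopsy". In Section 8.6, note 1 to Table 1 governs the same Screening column and reads: "Performed within 4 weeks prior to Leukapheresis Visit".

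**Biopsy to leukapheresis.** Section 6.1.2 gives a minimum: "The leukapheresis should not be performed less than 48 hours after the tumor biopsy procedure". Section 8.3 speaks in two ways. Its heading sets an upper limit, "Leukapheresis Visit (must occur within 3 weeks after biopsy", while the text below it names a point in time: "Leukapheresis for AGS-003 manufacturing should be performed 3 weeks after tumor biopsy". Section 8.3 also lets a second leukapheresis fall outside the 3 weeks without counting as a deviation.

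**Leukapheresis to first dose.** Section 8.4 states: "The manufacturing of the vaccine can take 6-12 weeks". It does not say what event starts that clock. Section 6.5 takes a patient off study if the product is delayed by more than 2 weeks.

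**Pregnancy.** Section 5.2, criterion 4, excludes: "Pregnant or nursing female patients". The synopsis lists the test as: "Pregnancy Test (urine) in females of childbearing potential: Screening and End of Study". Section 8.2, Section 8.5 and Table 1 agree with that schedule. The Injection Week #1 list in Section 8.4.1 contains no pregnancy test. Section 8.1 has eligibility settled before enrollment. Inclusion criterion 4 requires contraception throughout participation and asks a woman who suspects pregnancy to tell her physician at once.

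**The concern.** There are two separate issues. The first is that one column of the schedule carries two windows. A coordinator working from Section 8.2 and a monitor working from Table 1 can reach opposite conclusions about whether the same patient was screened in time.

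The second is that neither window is tied to first exposure. The product is made to order after biopsy and leukapheresis, so weeks to months pass between the check of the pregnancy exclusion and dose 1. The next scheduled test is at End of Study, about a month after nephrectomy, by which time a patient who completes treatment has had three doses and surgery. Pregnancy is also not named among the discontinuation reasons in Section 6.5, although investigator judgment is. At stake is whether an existing exclusion still holds, on verified information, when the product is first given.

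**Working it through.** The protocol states no interval from Screening to dose 1, so there is no figure to reproduce. The check adds up the protocol's own windows.

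**Inputs (weeks).**
- Screening lead: up to 4 before biopsy (Section 8.2), or up to 4 before leukapheresis (Table 1, note 1).
- Biopsy to leukapheresis: 48 hours = 2/7 ≈ 0.3 (Section 6.1.2), up to 3 (Section 8.3).
- Manufacturing: 6 to 12 (Section 8.4).
- Tolerated product delay: up to 2 (Section 6.5).

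**Anchor gap.** A patient screened 4 weeks before biopsy, with leukapheresis 3 weeks after it, was screened 4 + 3 = 7 weeks before leukapheresis. That is in window under Section 8.2 and 7 − 4 = 3 weeks out of window under note 1. Conversely, with leukapheresis at 3 weeks, note 1 leaves only 4 − 3 = 1 week before biopsy for Screening. The text of Section 8.3 names 3 weeks as the time of leukapheresis, so this is not a remote case.

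**Maximum age of the pregnancy test at dose 1.** This assumes that manufacturing time runs from leukapheresis.
- Note 1: age = 4 + manufacturing.
- Section 8.2: age = 4 + (biopsy to leukapheresis) + manufacturing.

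| Manufacturing | Note 1 | 8.2, leukapheresis at 48 h | 8.2, leukapheresis at 3 wk |
|---|---|---|---|
| 6 wk | 4 + 6 = 10 | 4 + 0.3 + 6 = 10.3 | 4 + 3 + 6 = 13 |
| 12 wk | 4 + 12 = 16 | 4 + 0.3 + 12 = 16.3 | 4 + 3 + 12 = 19 |

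**Shortest case under Section 8.2.** Test on the day of biopsy, leukapheresis at 48 hours, 6 weeks of manufacturing: 0.3 + 6 = 6.3 weeks.

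**Sensitivity.**
- Clock started at biopsy: the Section 8.2 maximum is 4 + 12 = 16 weeks, not 19.
- A 2-week delay on top of 12 weeks: 16 + 2 = 18 (note 1) and 19 + 2 = 21 (Section 8.2).
- A second leukapheresis outside the window could lengthen the interval further, with no stated limit.

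**Consistency with Section 4.2.** Participation is given as about 6 months, or about 26 weeks. The 19-week case plus 2 weeks to dose 3 plus about 4.3 weeks from nephrectomy to End of Study is 19 + 2 + 4.3 = 25.3 weeks, before any gap between dose 3 and surgery. It just fits.

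**The case against.** **The anchors can be met together.** A patient screened before biopsy and within 4 weeks of leukapheresis satisfies both rules. This stands. It makes the conflict a matter of wording, worth at most 3 weeks. It does not remove it, because nothing tells a site to apply both.

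**Pregnancy is already guarded against.** Inclusion criterion 4 requires contraception and prompt self-report. This also stands in part: it reduces the gap. It relies on adherence and on the patient suspecting pregnancy, and it does not establish status before dosing. The protocol does not say how many of the at most 10 patients could become pregnant, so the number affected may be very small.

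**The test schedule is consistent throughout.** True: the synopsis, Sections 8.2 and 8.5 and Table 1 agree. The gap lies between that schedule and the exclusion it serves, given the manufacturing time.

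**The 6-week floor is not firm.** If manufacturing started at biopsy and note 1 were read alone, Screening could fall on the day of leukapheresis, 3 weeks after biopsy, and the test could be 6 − 3 = 3 weeks old at dose 1. The floor is therefore stated only for Section 8.2.

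**A wider reading is tempting but not supported.** A reader might infer that all the exclusions are applied once and then lapse, so that a patient who had started chronic steroids or developed autoimmune disease would be dosed as written. The documents say otherwise. Section 6.4.2 prohibits chronic systemic corticosteroids on study. Section 8.4.1 repeats concomitant medications, adverse events and, before dosing, hematology, chemistry and autoimmunity tests. Sections 6.5 and 10.3 take patients with autoimmune disease off treatment or study. For infection, vital signs, a blood count with differential and C-reactive protein are collected at Injection Week #1, and Section 6.5 allows withdrawal on investigator judgment. Nor do the documents support a claim that the Screening window distorts the immune baseline, because that sample is drawn at Injection Week #1 before dosing.

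**Conclusion.** The point holds in two limited parts. First, Section 8.2 and note 1 to Table 1 give different windows for the same visit, up to 3 weeks apart, and Section 8.3 adds to this by stating both a limit of 3 weeks and a time of 3 weeks. Second, the pregnancy exclusion rests on one test before exposure. Its maximum age at dose 1 is 10 to 13 weeks if manufacturing takes 6 weeks and 16 to 19 weeks if it takes 12.

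These figures assume that manufacturing is counted from leukapheresis, that there is one leukapheresis, and that there is no product delay. A reader might take 16 to 19 weeks as the usual age of the test. It is not: it is the pair of worst cases under the two anchors at the longest manufacturing time, and the Section 8.2 maximum falls to 16 weeks if the clock starts at biopsy. Reconciling the anchors would not by itself close the second gap, since note 1 alone still allows 16 weeks.

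The anchor conflict is minor. The missing test is a small but real safety gap that is cheap to close, and it should be closed.

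**What to change.** 1. Reconcile Section 8.2, Section 8.3 and Table 1 note 1 to one Screening anchor and one statement of the biopsy-to-leukapheresis interval. Which window applies is for the sponsor to decide.
2. Align the pregnancy-test schedule with exclusion criterion 4: mark the existing urine test in the Injection Week #1 column of Table 1, in Section 8.4.1 and in the synopsis, before dosing, for the women to whom it already applies. Leave the action on a positive result to the sponsor.

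No general recheck of eligibility before dosing is asked for.

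The cost is one amendment and one extra urine test per woman concerned, at a visit that already includes blood draws, in a study of at most 10 patients. The downside is that a patient may occasionally be found pregnant after her product has been made.

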9 BIOLOGICAL SPECIMEN MANAGEMENT

9.1 Blood Sample Collection and Processing for Immunologic Analysis

9.1.1 Samples for Argos Immune Monitoring

Samples for immunologic analysis (six 10 mL green-top heparinized collection tubes) will be collected in the Phlebotomy Laboratory prior to the initial AGS-003 dose, after the 3rd dose, and at the final study visit. Samples will be sent to Laboratory Medicine for same day shipment to Argos Therapeutics, Inc. (Refer to Argos Immune Monitoring Sampling Kit Instructions and Immune Monitoring Sample Worksheet.) Immune monitoring samples are sent to the following address on the Day of Collection (Monday through Thursday):

Argos Therapeutics, Inc.
[name]

[contact]

9.1.2 Samples for Correlative Studies

Samples for the study correlative analyses (four 10 mL green-top heparinized collection tubes) will be collected in the Phlebotomy Laboratory at the same times as those for Immune Monitoring described above (prior to the initial AGS-003 dose, after the 3rd dose, and at the final study visit) and sent to the Hematological Procurement Facility.

Plasma and PBMC will be separated from the total blood within 30 minutes following the extraction. The screw cap polypropylene cryogenic tube will be labeled with the patient's MR number, patient's initials, patient's study number, clinical study number, protocol time point, dose, and protocol day. The label for each patient's sample will be supplied by RPCI. The samples will immediately be frozen at -70°C or below until analyzed and the PBMCs will be stored in liquid nitrogen. The samples will be stored in the Hematologic Procurement Facility and batch-shipped to [name] for analysis.

Samples will be analyzed in [name] laboratory:

Buffalo Life Sciences Complex (BLSC)
Center for Genetics and Pharmacology (CGP)
Laboratory location: L5-141
Lab [contact]
Lab contacts:

[name] [name] PhD-Lab Manager
[name], Assistant Professor, office number: [contact]
[name] [contact]

[name] office number: [contact]
[name] [contact]

Note: All investigator or analyzing research laboratories housing research samples need to maintain current **Temperature Logs** and study-specific **Sample Tracking and Shipping Logs**. The Principal Investigator/Laboratory Manager **must** ensure that the stated lab(s) have a process in place to document the receipt/processing/storage/shipping of study-related samples/specimens. This is required for both observational and interventional clinical studies collecting clinical samples.

Refer to **Section 13** for correlative data analysis.

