13 CORRELATIVE DATA ANALYSIS

Immune parameters will be assessed to demonstrate the effect of AGS-003 on the immune system. Immune effector cell populations will be assessed in a very detailed fashion and will focus on those populations that were found to be of interest in previous studies with AGS-003. Therefore, this study will analyze CD8⁺CD28⁺ T cells (REHA). In addition, this study will analyze T-regulatory cells (CD4⁺CD25⁺FoxP3⁺) and myeloid derived suppressor cells (MDSC) using multicolor flow cytometry. These cell populations will be assessed in peripheral blood specimens as well as in tumor lysates. The serum cytokine microenvironment will be assessed using multiplex Th1/Th2 cytokine ELISA (this will include IL-12 and IFN- γ). If perinephric lymph nodes are removed as standard of care during the kidney surgery, these will be procured and analyzed in a similar fashion. Autologous T cells will be incubated with irradiated autologous tumor cells and T cell proliferation will be measured in IFN- γ ELISPOT assays.

After appropriate tumor tissue has been procured to assure pathologic diagnosis, tumors will be processed into tumor lysates. These lysates will be analyzed using flow cytometry as described above. The tumor infiltrating immune cell populations and tumor cytokine microenvironment will be assessed using standard double-staining immunohistochemistry. These results will be compared to a historical control tissue microarray (TMA) that contains 264 RCC specimens.

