16.3 Confidentiality

Any data, specimens, forms, reports, video recordings, and other records that leave the site will be identified only by a participant identification number (Participant ID, PID) to maintain confidentiality. All records will be kept in a limited access environment. All computer entry and networking programs will be done using PIDs only. Information will not be released without written authorization of the participant.

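### Correlative blood tubes carry MR number and initials to a separately listed laboratory, against Section 16.3; separately, the printed time point leaves the before/after readings unmasked

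*Combined protocol and SAP*

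**What the plan says.** Section 9.1.2 covers the blood drawn for the correlative assays. Once plasma and PBMC are separated, the cryogenic tube is "labeled with the patient's MR number, patient's initials, patient's study number", followed by "clinical study number, protocol time point, dose, and protocol day". It adds: "The label for each patient's sample will be supplied by RPCI". On what happens next it says: "The samples will be stored in the Hematologic Procurement Facility and batch-shipped to" a laboratory that the section lists at the Buffalo Life Sciences Complex. No relabelling step comes between storage and shipment.

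Section 16.3 sets the confidentiality rule. Its scope is "Any data, specimens, forms, reports, video recordings, and other records that leave the site", and these "will be identified only by a participant identification number (Participant ID, PID) to maintain confidentiality".

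The readings serve the primary objective (Section 3.1), which is to assess systemic and intratumoral immune effects. Section 4.1 describes a non-randomized study in which every patient receives the same fixed dose. Section 12 models time as a three-level factor, tests for any time effect, and makes pairwise comparisons of visits only if that omnibus test is significant. Section 13 lists multicolor flow cytometry, cytokine ELISA and IFN-γ ELISPOT. Sections 9, 12 and 13 describe no masked reading, coded aliquots or random read order.

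**The concern.** Two separate matters meet on one label.

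The first is consistency. An MR number and initials identify a person and are not a participant ID. Staff who follow Section 9.1.2 and then ship the tube as labelled would depart from Section 16.3 if the receiving laboratory is off site.

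The second is measurement. There is no concurrent control, so the blood analysis rests entirely on comparing visits within patients. The visit is printed on the tube. Where a reading depends on judgment, as it can in setting flow gates or counting ELISPOT spots, a reader who knows which tube is post-dose may shift the result without intending to. In a before/after design such a shift cannot be separated from an effect of AGS-003. Because the samples are already frozen, stored centrally and shipped in batches, masking would be easy to arrange.

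**Working it through.** **Label against rule.** The protocol gives no figure on this point, so the first check is a comparison of the text.

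| Item on the tube (9.1.2) | Identifies a person? | At odds with 16.3 once off site? |
|---|---|---|
| MR number, initials | Yes | Yes |
| Patient's study number | By code | Not if it is the participant ID; the protocol does not say |
| Clinical study number | No (identifies the trial) | No |
| Time point, dose, protocol day | No | No, but time point and day reveal the visit |

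Section 16.3 therefore reaches MR number and initials only. Dose reveals nothing useful, since all patients receive the same one. Time point and protocol day are what disclose the contrast.

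**Illustration of reader bias.** The inputs come from Section 12.1: log-scale SD 0.68, within-patient correlation 0.50, at most 10 patients, two-sided 0.05. The bias is an assumption, because the documents give none.

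Checking the inputs: an original-scale mean of 100 and SD of 75 give a log variance of ln(1 + 0.75²) = 0.446. The log mean is then ln(100) − 0.446/2 = 4.38 and the log SD is √0.446 = 0.668, close to the stated 4.38 and 0.68. With 0.68, power for a shift from 4.38 to 5.08 is 82.5%, against the stated 80% (which is reached at 5.06). The inputs are therefore close to those the plan used.

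- SD of the log difference = 0.68 × √(2 × (1 − 0.50)) = 0.68.
- SE of the mean log change = 0.68/√10 = 0.215.
- Noncentrality for a proportional shift b = ln(1 + b)/0.215, with 9 df and critical value 2.262. This is 0.443, 0.848, 1.220 and 1.565 for b = 10%, 20%, 30% and 40%.

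The ungated column below is the exact noncentral-t result. The gated column is a simulation of three visits with the same SD and correlation (400,000 replicates per row, both post-dose visits shifted). It counts a rejection only if the omnibus F test and the paired test of the first post-dose visit against baseline are both significant at 0.05.

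| Assumed shift, no true effect | Ungated paired test rejects | One contrast after omnibus gate rejects |
|---|---|---|
| 0% | 5.0% | 2.3% |
| 10% | 6.8% | 3.6% |
| 20% | 11.8% | 7.1% |
| 30% | 19.4% | 13.0% |
| 40% | 28.8% | 21.3% |

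Shifting only the first post-dose visit gives nearly the same gated rates. Using the model's pooled error for the contrast, in place of a separate paired test, raises them to about 4%, 8%, 14% and 23%. A 5% shift gives 5.5% ungated. All rates are per marker; Section 12 makes no adjustment across markers.

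**The case against.** The case against a broad reading is good, and much of it stands.

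- A reader might infer that the two sections cannot both be followed. That goes too far. Section 9.1.2 labels the tube at processing and Section 16.3 applies when specimens leave, so relabelling before shipment would satisfy both. The site is also not defined. The defect is that the protocol neither provides the relabelling step nor says the laboratory is on site.
- A reader might infer that Section 16.3 forbids the time point. It does not: its subject is how the participant is identified. Masking has to be argued on its own merits.
- A reader might infer that all assays behind the primary objective are read unblinded. The documents do not say so. They name an objective and no single primary endpoint. The label rule covers correlative plasma and PBMC tubes only, and label content is not given for the manufacturer's monitoring tubes (9.1.1) or for nephrectomy tissue and slides (9.3, 9.4). Unmasked reading is an inference from a visible time point and the absence of any masking step. How gates are set and spots counted is not described, and ELISA leaves less to the reader.
- Section 13 says that "Immune parameters will be assessed to demonstrate the effect of AGS-003 on the immune system". This is ordinary wording and no evidence of bias.
- This is a pilot of at most 10 patients that openly forgoes overall Type I error control, and the size of the bias is assumed.

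The last point lowers the weight of the masking argument but does not remove it. Section 12 still declares significance at 0.05, and Section 2 says that the expected immune responses would lead to a larger Phase II study.

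**Conclusion.** The identifier conflict holds on the text, subject to one condition: the laboratory is off site and tubes are not relabelled before they go. Shipment to a separately listed complex points that way, but the protocol leaves both questions open, and Sections 9.1.2 and 16.3 should be reconciled.

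The masking point holds as a recommended improvement that Section 16.3 does not require. It concerns the correlative blood readings, and chiefly flow gating and ELISPOT counting. Its size is unknown. Under the protocol's own variability, a shift of about 5% would hardly matter, while shifts of 10% to 40% would give about 7% to 29% false rejections per marker ungated. For one contrast after the omnibus gate the range is about 4% to 21%, against 2.3% with no bias. These figures assume log-normal data, 10 complete patients and a uniform shift. They show sensitivity and do not estimate what would happen in this laboratory.

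**What to change.** 1. In Section 9.1.2, label shipped tubes with the participant ID plus a non-sequential aliquot code. Drop MR number, initials, time point, dose and protocol day. A participant ID alone would not do, because a patient's three draws could not be told apart. A random code alone would hinder the matching of autologous T cells to autologous tumor cells in Section 13, which the participant ID keeps possible.
2. Word Section 16.3 to allow the aliquot code, and state whether the analysing laboratory counts as on site.
3. Have the procurement facility hold the key from code to time point and release it to the statistician after readouts are locked.
4. Run each patient's frozen time points in one batch, in random order.

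The cost is a new label template and a code list kept by a facility that already stores the tubes; no extra samples or visits are needed. The downside is that the laboratory cannot check the visit sequence until the key is released. An error in the list would misassign visits unnoticed until then, so the facility must keep it accurate.
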